## **5.2 AGENT ADMINISTRATION**

---

Treatment will be administered in the MS center. The MS centers must have skilled personnel and adequate equipment to provide emergency treatment should the subject experience anaphylaxis, hypotension or respiratory distress. Subjects will be enrolled into a specified cohort. A single dose of 150 mg of ublituximab on Day 1 with an infusion rate of 4 hours, 450 or 600 mg on Day 15 at different infusion rates (see dosing scheme), and at week 24, a single dose of 450 or 600 mg of ublituximab with different infusion rates will be administered to the respective cohorts. Additionally, 2 subjects in each cohort will be randomized to a placebo group. On day 28, the placebo subjects will begin active treatment with ublituximab in its respective cohort (see dosing scheme). Administration of ublituximab and placebo will be under the direction of the study investigators. Additional dosing cohorts may be explored.

It is required the absolute neutrophil counts and the platelet count should be within normal range before the infusion of ublituximab.

If the liver enzymes (ALT and/or AST) are > 5 times the upper limit of normal (ULN) of the normal range, or if the neutrophil count and platelets counts are below acceptable levels as described, the dose of ublituximab will be held for up to 48 hours until the laboratory values return to within acceptable range. If all labs above do not return to within the acceptable range within 48 hours, the subject will not receive the ublituximab infusion and will be withdrawn from the study. Subjects who are withdrawn will be asked to enter the follow-up evaluation period of the study.

---

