## 6 DOSING DELAYS/DOSE MODIFICATION - RECOMMENDATIONS

Subjects should be assessed clinically for toxicity at each visit using the NCI CTCAE v4.0 (<http://evs.nci.nih.gov/ftp1/CTCAE/CTCAE>) grading scale.

Dosing will occur only if a patient's clinical assessment and laboratory test values are acceptable.

Dose modification and or intervention with supportive care recommendations for ublituximab is provided below, however final discretion lies with the treating investigator in regards to more or less aggressive intervention, if the investigational agent needs to be reduced, and actual dose reductions, as well as the number of dose reductions.

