### 6.1 CRITERIA FOR ONGOING TREATMENT

Repeat treatment should be administered per protocol provided that:

- Renal function should continually be assessed, with appropriate dose modifications as needed
- Recovered from grade 3-4 non-hematologic toxicity to grade 2 or less.
- Treatment may be delayed to recover from toxicity or per investigator discretion.
- No clinical or radiographic evidence of disease progression.

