##### 6.2.1.1 LAB ABNORMALITIES

**If cytopenias are deemed related to the underlying disease rather than ublituximab, dose reductions are not required, or are per investigator discretion.**

Worst CTCAE Grade Toxicity	Action to be Taken
Neutropenia	
Grade	Management
≤ Grade 1	No action required.
Grade 2	No action required; consider growth factor support.
Grade 3 or 4 1 st Occurrence	Hold until < Grade 3. Consider growth factor support per protocol requirement. Resume ublituximab at current dose cohort. Hold until < Grade 3. Consider growth factor support per protocol requirement. Resume ublituximab at current dose cohort.
Grade 3 or 4 subsequent Occurrences	Hold until < Grade 3. Consider growth factor support. Resume ublituximab at current dose cohort.
Management of neutropenia are per institution guidelines and if in the opinion of treating investigator, are appropriate for patient care.	

Worst CTCAE Grade Toxicity	Action to be Taken
Thrombocytopenia or Anemia	
Grade	Management
≤ Grade 1	No action required.
Grade 2	No action required.
Grade 3 or 4 1 st Occurrence	Hold until < Grade 3, or at subjects previous baseline. Resume ublituximab at current dose cohort.
Grade 3 or 4 subsequent Occurrences	Hold until < Grade 3, or at subjects previous baseline. Resume ublituximab at current dose cohort.
Management of thrombocytopenia and anemia are per institution guidelines and if in the opinion of treating investigator, are appropriate for patient care.	

Worst CTCAE Grade Toxicity	Action to be Taken
Elevated Liver Enzymes	
Grade	Management
≤ Grade 1	No action required.
Grade 2	No action required.
Grade 3 or 4 1 st Occurrence	Hold until < Grade 1, or at subjects previous baseline. Resume ublituximab at current dose cohort.
Grade 3 or 4 subsequent Occurrences	Hold until < Grade 3, or at subjects previous baseline. Resume ublituximab at current dose cohort.
Management of elevated liver enzymes are at the discretion of the investigator and should be discussed with TG Therapeutics.	

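### For low neutrophils or platelets before the Day 15 or Week 24 infusion, Protocol 5.2 and 6.2.1.1 give opposite instructions with no order of precedence, so one Day 15 event can be a delay DLT or a replaced withdrawal

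*Protocol*

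**What the plan says.** **Protocol 5.2 (Agent Administration)** sets a sequence for every ublituximab infusion.

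- The condition: "It is required the absolute neutrophil counts and the platelet count should be within normal range before the infusion of ublituximab".
- If it is not met, "the dose of ublituximab will be held for up to 48 hours until the laboratory values return to within acceptable range".
- If the counts have not recovered by then, the subject "will not receive the ublituximab infusion and will be withdrawn from the study". Withdrawn subjects are asked to enter follow-up.

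**Protocol 6.2.1.1 (Lab Abnormalities)** covers the same counts when the investigator attributes the toxicity to ublituximab.

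- Grade 2 neutropenia: "No action required; consider growth factor support". Grade 1 neutropenia, and Grade 1 or 2 thrombocytopenia, likewise call for nothing.
- Grade 3 or 4: hold until the count is below Grade 3, then continue at the same dose. The row for repeat neutropenia ends "Consider growth factor support. Resume ublituximab at current dose cohort". The thrombocytopenia rows add a return to the subject's own baseline as an alternative: "or at subjects previous baseline. Resume ublituximab at current dose cohort". No row gives a maximum hold.

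Section 6.1 adds: "Treatment may be delayed to recover from toxicity or per investigator discretion". The opening of Section 6 presents its content as recommendations, where "final discretion lies with the treating investigator in regards to more or less aggressive intervention". Neither 5.2 nor Section 6 refers to the other on this point.

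**Protocol 5.1.1** lists a treatment delay of at least 14 days for unresolved toxicity as a DLT. Neutropenia is a DLT in its own right only at Grade 4 for more than 7 days, or when febrile at Grade 3 or above. **Section 3.3** says a subject who withdraws in the first 4 weeks for a non-DLT reason will be replaced; **5.1.2** says may be.

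**The concern.** A site that finds a low count at the pre-infusion check has two instructions that cannot both be followed. At Grade 2, 5.2 forbids the infusion and ends participation after 48 hours, while 6.2.1.1 calls for no change. At Grade 3-4, 5.2 stops after 48 hours, while 6.2.1.1 waits as long as recovery takes and then doses.

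The Day 15 check matters most. Day 15 is the only repeat infusion inside the 4-week DLT window, so the rule a site follows can decide whether a drug-related toxicity enters its cohort's DLT count or leaves as a withdrawal to be replaced. At Week 24 the conflict affects dosing and withdrawal but not DLTs, because the window has closed.

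**Working it through.** The plan gives no figure to reproduce here. The check follows one subject through both rules.

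**Inputs**
- Maximum hold: 48 hours = 2 days (5.2); none stated (6.2.1.1).
- Delay DLT: 14 days or more (5.1.1).
- DLT window: first 4 weeks of treatment (5.1.1).
- Subjects assigned to ublituximab per cohort: 6 (5.1, Table 6).

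**Case A: Grade 3 neutropenia, no fever, possibly related, present on Day 15 and lasting at least 14 days**

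| Step | 5.2 governs | 6.2.1.1 governs |
|---|---|---|
| Hold ends | Day 15 + 2 = Day 17, withdrawn | Not before Day 15 + 14 = Day 29 |
| Neutropenia DLT by grade | Not met | Not met |
| 14-day delay DLT | Not reached: 14 − 2 = 12 days short | Reached on Day 29 |
| Replacement | Will be (3.3) or may be (5.1.2) | None: the reason is a DLT |
| Cohort DLT count | 0 of 6 evaluable | 1 of 6 |

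Day 29 is 29 − 1 = 28 days after Day 1, the edge of the window. The toxicity itself starts by Day 15, inside it. If Day 29 were ruled out, a delay starting at the scheduled Day 15 infusion could never satisfy the criterion.

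The 0 of 6 assumes that a replacement completes the evaluation and that the withdrawn subject does not meet the 4-week safety requirement in 5.1.2. If the withdrawn subject does meet it, or if the table uses the SAP Safety Population (SAP 2.2.1 and 2.4.5.1), the figure is 0 of 7.

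**Size for one cohort (exact 95% limits)**
- 1/6 = 16.7%, limits 0.4% to 64.1%.
- 0/6: upper limit 1 − 0.025^(1/6) = 45.9%.
- 0/7: upper limit 1 − 0.025^(1/7) = 41.0%.

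The intervals overlap widely. What changes is whether the count is one or zero.

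**Case B: Grade 4 neutropenia for 5 days, no fever, present on Day 15, below Grade 3 within 14 days**

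This is not a DLT under either rule, and 10.4 lists Grade 4 neutropenia of under 7 days without fever as expected. Section 6.2.1.1 holds and then resumes. Section 5.2 withdraws the subject on Day 17. The outcome for the subject differs, and no question about Day 29 arises.

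**The case against.** The strongest reply is that the sections can be ranked. Section 5.2 is worded as a requirement, while Section 6 is headed as recommendations, yields to the investigator, and opens by making dosing conditional on acceptable laboratory values. On this view a no-action entry in a dose-modification table is not an order to infuse after a failed pre-infusion check, and the 14-day delay criterion still works for other toxicities.

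Much of this is fair, and 5.2 governing is the more natural ranking. But the documents do not state it, and it leaves a problem. The Grade 3-4 rows tell the site to resume once the count is below Grade 3, which includes Grade 2, a level that 5.2 does not allow. Those rows would have no effect beyond 48 hours, and a count-based hold could not reach the delay DLT. One could argue that a dose never given is delayed indefinitely, but 5.1.1 does not say so.

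Three further limits stand. Section 5.1.1 lets the study team class other events as DLTs, or decline to class a listed one. Replacement is mandatory in 3.3 but optional in 5.1.2. The withdrawn subject stays in the Safety Population, and under 5.1.3 the DSMB reviews all adverse events and the total safety data.

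Two stronger readings are tempting. A reader might infer that the primary Week 4 responder denominator shrinks. The documents do not establish this: withdrawn subjects are asked to enter follow-up and may have a Week 4 value, SAP 2.2.2 keeps anyone dosed once in the ITT population, and a replacement may be added. A reader might also infer a frequency from Protocol 8.1.1.1, which lists neutropenia and thrombocytopenia as common (>20%) with single-agent ublituximab. That list does not separate MS subjects, grade, duration or a Day 15 time point, so it gives no rate for Case A.

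**Conclusion.** The conflict is real and minor. Two current rules give incompatible instructions for the same low count at two of the three infusions, and no sentence ranks them. If 5.2 governs, its combination with 3.3 takes a persistent drug-related Grade 3 neutropenia out of the listed DLTs and treats it as a withdrawal to be replaced. If 6.2.1.1 governs, the same event can become a delay DLT.

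The difference is one event in a cohort of 6: 1 of 6 against 0 of 6 evaluable (or 0 of 7). It rests on three assumptions: the neutropenia is at least possibly related and lasts 14 days or more from Day 15; a delay completing on Day 29 counts because the toxicity began inside the window; and the study team does not use its discretion to reclassify the event.

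It would go too far to say that the event is always a DLT under one rule and always lost under the other, or that it would be hidden. The DSMB still sees it, and with no numeric DLT threshold no escalation boundary is crossed or missed. The effect is on dosing, withdrawal, replacement and the by-cohort DLT tables.

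**What to change.** 1. Write one pre-infusion rule for neutrophils and platelets by CTCAE grade, and use it in both 5.2 and 6.2.1.1. It should state which grades are dosed, how long a hold may last and when the subject stops.
2. Set the maximum hold to fit the 14-day delay DLT in 5.1.1. If a shorter limit is kept, say whether an infusion omitted for drug-related toxicity counts as a DLT.
3. State in 3.3 and 5.1.2 that a subject stopped in the first 4 weeks for a drug-related low count remains DLT-evaluable, goes to DLT review and is not replaced as a non-DLT withdrawal. Use the same verb for replacement in both places.

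The cost is one paragraph in 5.2, matching text or a cross-reference in 6.2.1.1, and one sentence each in 3.3 and 5.1.2. No new data are collected.

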### **5.2.1 GUIDELINES FOR ADMINISTRATION OF UBLITUXIMAB**

---

- *Necessity of MS Center:* Center must have personnel and equipment necessary to provide adequate emergency treatment for anaphylaxis, hypotension and respiratory distress.
- *Method of Administration:* Ublituximab must be administered as an intravenous infusion through a dedicated intravenous line and will be done under the supervision of the study investigator
- *Potential Drug Interactions:* No drug interactions have been reported to date.
- *Pre-medications:* Pre-medicate approximately 30 minutes prior to each dose of ublituximab with an antihistamine (diphenhydramine 50 mg or equivalent), and corticosteroid (dexamethasone 10-20mg or equivalent). Oral acetaminophen, 650 mg (or equivalent; only used for intervention) should be restricted to patient who experience fever or pyrexia after week 1 dose, or as clinically warranted and additional medication (which needs to be documented) may be used at discretion of the physician if adverse reactions occur.

- *Hypersensitivity and Infusion Reaction Precautions:* Medication and resuscitation equipment utilized by a trained personnel must be available per institutional guidelines prior to ublituximab administration for the emergency management of potential anaphylactic reactions
- *Subject Care Implications:*
  - Ublituximab should not be administered as an IV push or bolus.
  - Ublituximab should only be diluted in 0.9% NaCl.
  - Diluted ublituximab should be checked before administration for cloudiness, color, or deposits. Ublituximab should not be administered if it does not conform to the manufacturer's specifications. The Monitor/Sponsor must be informed immediately of any quality concerns or questions about the product.
  - It is recommended that ublituximab be administered immediately after dilution.
  - No other treatment may be co-administered with ublituximab (other than for immediate intervention for adverse event).

#### 5.2.1.1 INFUSION RELATED REACTIONS AND INFUSION RATE GUIDANCE

---

Infusion related reactions, including severe reactions, have been reported with ublituximab administration in subjects with CLL and NHL. Guidelines are provided below for subjects who experience such reactions. Symptomatic infusion reactions, despite premedication, may be treated at the discretion of the Principal Investigators using the following or other appropriate treatments: oral acetaminophen 650 mg, corticosteroids, antihistamines, oxygen, and bronchodilators.

The following are recommended infusion rate reduction/delay guidelines for subjects who experience severe Infusion Related Reactions (IRR's) that require treatment interruption. The final decision for the infusion rate reduction/delay or discontinuation resides with the treating investigator. Infusion rates should be considered targets for each respective cohort. If the treating investigator decides to interrupt the infusion or slow the infusion rate, then the reduction/delay and the reason for it must be noted on the eCRF and infusion log.

##### **Infusion Interruption:**

- Stop the infusion, and closely monitor the subject. Institute symptomatic medical management until resolution of IRR symptoms.
- Following the judgment of the investigator and provided the subject is stable, the infusion may be resumed at no more than half the previous rate.

If the subject does not experience any further IRR symptoms, the infusion may be resumed at the increments and intervals as appropriate for the treatment dose.

If there is a second interruption of treatment due to IRR symptoms, ublituximab infusion must be stopped. The treating physician may decide whether to attempt completion of the infusion on a second day.

#### 5.2.1.2 DISPENSING OF UBLITUXIMAB

---

Before dispensing, the site pharmacist or his/her representative must check that the ublituximab product received is in accordance with the product specifications and the re-test/expiration date.

The exact dose, date and time of administration of ublituximab must be recorded within the CRF, the subject's medical records and/or in the drug accountability records.

The pharmacist or his/her representative should complete the accountability forms with information concerning the dispensation of ublituximab. Preparation should be done by the pharmacist or his/her representative according to instructions for sterile dilution provided below.

The pharmacist or his/her representative should record the date dispensed and the subject's study identification number and initials, as well as complete the accountability forms with information concerning the dispensation of ublituximab. Preparation should be done by the pharmacist or his/her representative according to instructions for sterile dilution.

### 5.3 GENERAL CONCOMITANT MEDICATION AND SUPPORTIVE CARE GUIDELINES

---

The following treatments are prohibited while on clinical trial: other investigational drug treatments or study participation, other DMTs used to treat MS, radiation therapy, hormonal therapy for cancer, cancer immunotherapy or other biologic therapy excluding trial drugs.

- No glucocorticoids may be administered outside of protocol requirements for premedication or AE management, except low doses of steroids stabilized at  $\leq 10$  mg per day of prednisone or equivalent, and started at least 7 days prior to study entry.

**Neutropenia:** Granulocyte colony stimulating factor (G-CSF; filgrastim or pegfilgrastim) may be used during the course of the study after the first 28 days during the dose-escalation portion, at the investigator discretion. The drug(s) should be used at a dose/schedule specified in the package insert. During the cohort expansion, GCSF may be used at the discretion of the investigator.

**Antiemetics:** Ublituximab is considered to be of low emetogenic potential that may be adequately prevented with prochlorperazine. Other antiemetics may be used at the discretion of the treating physician if nausea and/or vomiting is not adequately controlled/prevented.

**Infusion Reactions with ublituximab:** Infusion related reactions have been reported with ublituximab, more profound in patients with hematologic malignancies. All subjects treated with ublituximab require pre-medication approximately 30 minutes prior to each dose of ublituximab with an antihistamine (diphenhydramine 50 mg or equivalent), and a corticosteroid (dexamethasone 10-20 mg or equivalent). Symptomatic infusion reactions despite premedication, may be treated at the discretion of the treating physician, including but not limited to: oral acetaminophen 650 mg (only used for intervention), corticosteroids, antihistamines, oxygen and bronchodilators.

#### **MS Relapses during the study:**

Any patient experiencing a multiple sclerosis relapse while on study will be allowed rescue therapy with intravenous methylprednisolone 1gm/day for up to 5 consecutive days. Subjects requiring rescue therapy will have an MRI scan 10 days after completion of treatment with steroids.

#### **Re-consent criteria**

In case of a confirmed diagnosis of MS relapse (as defined in the protocol, Appendix C), **or** in case of an increase in EDSS of 1.0 points or more, sustained for at least 3 months, during the study, the following actions will be taken:

1. The subject will be reminded of the current approved MS medications/treatments and the opportunity to terminate the study and be treated with an approved MS medication.
2. The subject will be requested to re-sign an informed consent form if he/she chooses to continue to participate in the study, in the same treatment assignment.

Subjects enrolled into the study will be closely monitored through the study course by the Sponsor's personnel as well as by an external independent data monitoring committee (DSMB) in order to ensure subjects' welfare.

## 5.4 DURATION OF THERAPY

---

In the absence of treatment delays due to adverse event(s), treatment should continue through first 24 weeks and beyond unless one of the following criteria applies:

- Disease progression or inter-current illness that prevents further treatment,
- Patient decides to withdraw from the study, or changes in the patient's condition render the patient unacceptable for further treatment in the judgment of the investigator.

The first efficacy assessment should be approximately 24 weeks after Day 1 ( $\pm 7$  days) and approximately another 24 weeks thereafter ( $\pm 7$  days) through the first 48 weeks following initiation of therapy.

The reason for study removal and the date the patient was removed must be documented in the Case Report Form. Subjects who discontinue therapy due to an adverse event should be followed until disease progression.

## 5.5 END OF STUDY/OPEN LABEL EXTENSION STUDY

---

Subjects who are in good health with stable disease and has completed the treatments and scheduled assessments through the final study visit may have the option of entering a 112 week open label extension study, with a continuation of treatment, and relapse and safety monitoring. The criteria for entering the open label extension study will be clearly stated in a separate protocol (TG1101-RMS201E).

## 6 DOSING DELAYS/DOSE MODIFICATION - RECOMMENDATIONS

Subjects should be assessed clinically for toxicity at each visit using the NCI CTCAE v4.0 (<http://evs.nci.nih.gov/ftp1/CTCAE/CTCAE>) grading scale.

Dosing will occur only if a patient's clinical assessment and laboratory test values are acceptable.

Dose modification and or intervention with supportive care recommendations for ublituximab is provided below, however final discretion lies with the treating investigator in regards to more or less aggressive intervention, if the investigational agent needs to be reduced, and actual dose reductions, as well as the number of dose reductions.

### 6.1 CRITERIA FOR ONGOING TREATMENT

Repeat treatment should be administered per protocol provided that:

- Renal function should continually be assessed, with appropriate dose modifications as needed
- Recovered from grade 3-4 non-hematologic toxicity to grade 2 or less.
- Treatment may be delayed to recover from toxicity or per investigator discretion.
- No clinical or radiographic evidence of disease progression.

### 6.2 IMPORTANT DOSE MODIFICATIONS

For RMS subjects, the hematologic dose modifications are graded by the CTCAE v4.0 (<http://evs.nci.nih.gov/ftp1/CTCAE/CTCAE>).

#### 6.2.1 DOSE MODIFICATIONS OF UBLITUXIMAB

If toxicity, in the opinion of the investigator, is attributable to ublituximab, the following guidelines for neutropenia, thrombocytopenia, anemia, and elevated liver enzymes are recommended below (for Infusion Related Reactions, see Section 6.2.1.2). Final discretion lies with the treating investigator in regards to more or less aggressive dose reductions, as well as the number of dose reductions.

